**Table 6: ECG Thresholds and Ranges**

Heart Rate (bpm)	Heart Rate Change from Baseline (bpm)	PR Interval (msec)	PR Percent Change From Baseline	QRS Interval (msec)	QTcF (msec)	QTcF Change From Baseline (Msec)
$> 120$	$\geq 20$	$\geq 200$	$\geq 15\%$	$\geq 120$	Males:	$\leq 30$
$> 130$	$\geq 30$	$\geq 220$	$\geq 25\%$		$< 430$	$> 30, \leq 60$
					$\geq 430$	$> 60$
					$\geq 450$	
					$\geq 470$	
					$\geq 480$	
					$\geq 500$	
					Females:	
					$< 450$	
					$\geq 450$	
					$\geq 470$	
					$\geq 480$	
					$\geq 500$	

## 8.7. Incidence of Falls

The numbers and percentages of subjects with at least one fall during the interval beginning on Study Day 1 and ending on Day 189 (the end of the Week 26 analysis window) will be provided, together with the corresponding numbers and percentages of subjects with at least one fall or near-fall.

In addition, the following categorical summaries with counts and percentages will be provided for falls and falls + near-falls:

- None
- 1
- 2
- 3 or more

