**Analysis:**

The FAS (Full Analysis Set) and Safety analysis set will be identical and is defined as all enrolled subjects who have received at least one dose of TD-9855 in this study.

Descriptive summaries will be provided for demographics and baseline characteristics.

Safety data will be listed by subject and summarized using the frequency of event or descriptive statistical summaries, as appropriate. Summary tables will be provided for adverse events, hematology, biochemistry and urinalysis laboratory evaluations, vital signs, 12 lead ECG findings, and concomitant medications.

Incidence of falls will be descriptively summarized using number of falls per subject, number and percentage of subjects with at least 1 fall since the previous study visit.

[REDACTED]

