### SCHEDULE OF STUDY PROCEDURES

**Table 1: Schedule of Study Procedures (Visits 1 – 6)**

Each study visit for each subject may be conducted either in clinic or remotely									
Study Week (Visit/Telephone):	Week 0 Visit 1 (0170 Visit 9)	Week 2 Visit 2 +/- 3 days	Week 6 Visit 3 +/- 3 days	Week 10 Visit 4 +/- 7 days	Week 14 Telephone 1 +/- 3 days	Week 18 Visit 5 +/- 7 days	Week 22 Telephone 2 +/- 3 days	Week 26 Visit 6 +/- 7 days	Early Termination up to Week 26
Informed Consent	X								
Inclusion / exclusion criteria	X								
Medical history, including smoking history	X								
Concomitant Medications	X a	X	X	X	X	X	X	X	X
C-SSRS	X a	X	X	X		X		X	X
[REDACTED]	[REDACTED]	[REDACTED]	[REDACTED]	[REDACTED]		[REDACTED]		[REDACTED]	[REDACTED]
Vital signs (heart rate, blood pressure, respiratory rate and body temperature)	X a, b	X b	X b	X b		X b		X b	X b
Physical examination	X a			X				X	X
Neurological examination	X a			X				X	X
12-lead electrocardiogram e	X a			X				X	X
Pregnancy Test	X a, c			X c				X c	X c
Safety Labs (chemistry, hematology, urinalysis)	X a			X				X	X
Dosing, Incidence of Falls, and Midodrine Diaries	X a	X	X	X		X		X	X
Adverse Events	X a	X	X	X	X	X	X	X	X
Dispense Study Drug	X d	X d	X d	X d		X d		X d	
Study Drug Dosing	X d								
Collect Study Drug		X	X	X		X		X	X

a. Study 0170 procedures conducted at Visit 9 will serve as the baseline assessment for Visit 1 of Study 0171.  
 b. Vital signs will be assessed after the subject has been resting for at least 5 minutes in the seated or supine position.

- c. In women of childbearing potential only, urine beta human chorionic gonadotropin ( $\beta$ hCG) test will be performed and if positive, confirmation with serum  $\beta$ hCG test is required. The pregnancy test must be confirmed negative for a subject to be eligible for this study.
- d. Study drug will be ingested in the morning at approximately the same time of day with 8 ounces of water. The exact time and day of dosing will be recorded on the mornings of study visits. Subjects must be reminded to maintain an adequate fluid intake during their scheduled visits. Subjects will start taking study drug on the day after Visit 1.

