#### **6.4.3.8. Incidence of Falls Diary**

Falls in subjects with symptomatic nOH are common and potentially catastrophic. They can lead to serious injuries including hip fractures or head trauma; furthermore, fear of falling can limit mobility and physical activity. Thus, incidence of patient-reported falls is being captured in a diary. Assessments will be performed as specified in the Schedule of Study Procedures ([Table 1](#)). An example of the diary is provided in [Appendix 2](#).

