**8.5.7. Analysis of Falls**

Incidence of falls will be descriptively summarized using number of falls per subject, number and percentage of subjects with at least 1 fall since the previous study visit.

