#### **3.2. Endpoints**

##### **3.2.1. Primary Study Endpoints**

Primary safety and tolerability endpoints include:

- Physical examination
- Neurological examination
- Vital signs
- Resting ECGs
- Clinical laboratory tests including biochemistry, hematology, and urinalysis
- Concomitant medications
- AEs
- Subject compliance to study treatment
- Incidence of falls
- Columbia Suicide Severity Rating Scale (C-SSRS)

[REDACTED]

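### SAP 8.7 drops the protocol's by-visit falls summary without explanation and caps falls per subject at 3 or more over one window, with no adjustment for exposure

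*SAP*

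**What the plan says.** SAP 3.2.1 lists "Incidence of falls" among the primary safety and tolerability endpoints. Protocol 6.4.3.8 gives the reason for collecting them: "Falls in subjects with symptomatic nOH are common and potentially catastrophic". It states no rate.

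Protocol 8.5.7, repeated in the synopsis, plans a descriptive summary by "number of falls per subject, number and percentage of subjects with at least 1 fall since the previous study visit".

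SAP 8.7 plans four outputs, all over one window:
- the number and percentage with "at least one fall during the interval beginning on Study Day 1 and ending on Day 189", the day on which the Week 26 analysis window closes;
- the corresponding figures for "subjects with at least one fall or near-fall";
- a count distribution (None, 1, 2, 3 or more) for falls;
- the same distribution for falls plus near-falls.

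It contains no by-visit summary, no mean or median count, no rate and no rule for subjects with shorter follow-up. SAP 2 says the sponsor terminated the study early with 110 subjects enrolled.

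**The concern.** In a single-arm extension the course over time is the main signal available inside the study. The protocol's by-visit percentage was the one falls output that could show it, and it is missing from SAP 8.7. What remains is a whole-period table in which a subject with 3 falls and a subject with 30 look the same.

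Falls are the exception within this SAP. Laboratory values (8.4), vital signs (8.5), categorical ECG (8.6) and C-SSRS (8.8) are summarised by visit. Rescue midodrine (8.3) gets a rate per 28 days and categories running past 20 uses. Where the SAP departs from plan because of early termination, it says so (Sections 5 and 6.1.3), but 8.7 gives no reason.

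Early termination adds a second problem. The chance of at least one fall grows with time observed, so a percentage that pools subjects with short and full follow-up partly measures how long they were watched. If many subjects stopped before Week 26, the table could look reassuring for that reason alone.

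**Working it through.** The plan gives no fall rate, power or target for falls, so there is no figure to reproduce. The rates below are assumptions.

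**Inputs from the documents.** The SAP 8.7 window is 189 days, or 189/28 = 6.75 periods of 28 days. Diaries are collected at Weeks 2, 6, 10, 18 and 26 (Protocol Table 1), giving intervals of 14, 28, 28, 56 and 56 days, 182 in total. Protocol Table 2 lists no falls diary after Week 26.

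**Formulas.** With mean count m:
- Poisson: P(any) = 1 − e^(−m); P(3 or more) = 1 − e^(−m)(1 + m + m²/2).
- Negative binomial with size k (smaller k means more variation between subjects): P(any) = 1 − (k/(k+m))^k. For k = 1, P(3 or more) = (m/(1+m))³.

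**1. Change over time.** Compare two Poisson profiles over the five intervals, in falls per 28 days.
- Rising: 0.5, 0.5, 0.75, 1.0, 1.5. Interval means 0.25 + 0.5 + 0.75 + 2.0 + 3.0 = 6.5.
- Flat: 1.0 throughout. Interval means 0.5 + 1.0 + 1.0 + 2.0 + 2.0 = 6.5.

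Both have the same whole-period result: any fall 1 − e^(−6.5) = 99.8%; 3 or more 1 − e^(−6.5)(1 + 6.5 + 21.125) = 95.7%. A table of the SAP 8.7 kind cannot tell them apart. By interval they differ:

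| Interval to | Week 2 | Week 6 | Week 10 | Week 18 | Week 26 |
|---|---|---|---|---|---|
| Rising, % with any fall | 22 | 39 | 53 | 86 | 95 |
| Flat, % with any fall | 39 | 63 | 63 | 86 | 86 |
| Rising, falls per 28 days | 0.5 | 0.5 | 0.75 | 1.0 | 1.5 |
| Flat, falls per 28 days | 1.0 | 1.0 | 1.0 | 1.0 | 1.0 |

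In the second row the flat rate appears to climb from 39% to 86% only because the intervals lengthen. The protocol's percentage therefore needs a rate beside it.

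**2. Shortened follow-up.** At a constant 0.5 falls per 28 days:

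| Followed to | m | Any fall, Poisson | Any fall, k = 0.5 |
|---|---|---|---|
| Day 42 | 0.75 | 53% | 37% |
| Day 98 | 1.75 | 83% | 53% |
| Day 189 | 3.375 | 97% | 64% |

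If half the subjects stopped at Day 42 for reasons unrelated to falls, the pooled figure would be (52.8 + 96.6)/2 = 74.7% under Poisson, against 96.6% with full follow-up. With k = 0.5 it would be (36.8 + 64.1)/2, about 50%, against 64%. The risk is the same in each comparison.

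**3. Ceiling.** Doubling the rate from 0.5 to 1.0 per 28 days moves the 189-day mean from 3.375 to 6.75:

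| Model | Any fall | 3 or more |
|---|---|---|
| Poisson | 96.6% to 99.9% | 65.5% to 96.4% |
| Negative binomial, k = 1 | 77.1% to 87.1% | 45.9% to 66.1% |
| k = 0.5 | 64.1% to 73.7% | 38.2% to 53.0% |
| k = 0.25 | 48.8% to 56.5% | 29.9% to 39.7% |

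Under Poisson the any-fall percentage has almost no room left from about 0.5 per 28 days, and the top category from about 1 (96.4% to 100% when 1 doubles to 2). At 0.1 per 28 days any-fall is only 49%. With strong variation between subjects both measures are blunted but not at a ceiling.

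**The case against.** The case for SAP 8.7 has real substance.

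- **The change is allowed.** Protocol 8.1 lets the SAP alter planned analyses before data lock, falls carry no test or decision rule, and a terminated study may reasonably report less. This stands, but permission is not a reason, and none is given for falls.
- **Falls per subject is partly kept.** A reader might infer that the SAP replaces everything with one any-fall percentage. It does not. The four-level table is a summary of falls per subject, the protocol does not demand an uncapped one, and the near-fall outputs go beyond the protocol's analysis text. What is lost is the by-visit output and the detail beyond 3 falls.
- **Saturation is not shown.** A reader might infer from the word common in Protocol 6.4.3.8 that the measures sit at their ceiling and could not register more falls. The documents give no rate. In the doubling example the 3-or-more share still moves by 31 points (Poisson) or 20 points (k = 1).
- **No baseline was removed.** Protocol Table 1 attaches to the diaries row the note that "Study 0170 procedures conducted at Visit 9 will serve as the baseline assessment for Visit 1 of Study 0171", so a reader might infer that a planned baseline comparison was dropped. Protocol 8.5.7 never included one. The Visit 1 procedures (Protocol 6.3.2) list dispensing the falls diary, not collecting one. Whether Study 0170 kept a comparable diary cannot be judged from these documents. SAP 7.5 shows that subjects come from a randomized withdrawal period, so a pooled baseline could mix treatments.
- **The data survive.** SAP 6 lists all visit data by subject, and injuries can surface as adverse events. The loss is in the summaries. Listings for up to 110 subjects are still a poor substitute for a summary of a primary safety endpoint.

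**Conclusion.** The point holds for the summary tables. SAP 8.7 omits the protocol's by-visit falls output without explanation and caps the count at 3 or more over one window. Those tables cannot show change over time within the study or separate subjects beyond 3 falls; both follow from the text and need no assumed rate.

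The lack of exposure adjustment is also a matter of text, but its size depends on two unknowns: the fall rate, and how many subjects had less than 26 weeks of diary. At an assumed 0.5 falls per 28 days, the any-fall percentage differs between Day 42 and Day 189 by about 44 points (Poisson) or 27 points (k = 0.5).

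Whether the measures also approach a ceiling stays open, because it turns on fall rates and between-subject variation that the documents do not give. Nothing here suggests that data are lost or that the sponsor went beyond what the protocol permits. It is a reporting gap worth closing because the endpoint is primary and the remedy is cheap.

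**What to change.** Keep the Day 1–189 tables in SAP 8.7 and add:

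- (a) an uncapped continuous summary of falls per subject, with falls per 28 diary-days of exposure;
- (b) for each between-visit interval (to Weeks 2, 6, 10, 18 and 26), among subjects with a returned diary, falls per 28 diary-days beside the protocol's number and percentage with at least 1 fall, with a note that the intervals run from 14 to 56 days.

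The percentage in (b) should not stand alone, because it rises with interval length even at a constant rate. If the sponsor prefers not to add these, SAP 8.7 should say why the protocol's by-visit output was dropped.

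A baseline comparison is optional, and only if comparable Study 0170 diary data exist. It should then be shown by prior randomized-withdrawal treatment.

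The cost is SAP wording and one or two extra descriptive tables from diaries already collected. One limit remains: a time trend in a single-arm study cannot separate drug effect from disease progression, and the added tables should say so.

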## 8.8. Columbia-Suicide Severity Rating Scale (C-SSRS)

The C-SSRS is a tool designed to systematically assess and track suicidal AEs (suicidal behavior and suicidal ideation). The strength of this suicide classification system is in its ability to comprehensively identify suicidal events while limiting the over-identification of suicidal behavior. The C-SSRS Since Last Visit Version will be used in this study.

The following 11 C-SSRS categories include 5 subtypes of suicidal ideation (1–5), 5 subtypes of suicidal behavior (6–10), and self-injurious behavior without suicidal intent. They all have binary responses (yes/no).

1. Wish to be Dead
2. Non-specific Active Suicidal Thoughts
3. Active Suicidal Ideation with Any Methods (Not Plan) without Intent to Act
4. Active Suicidal Ideation with Some Intent to Act, without Specific Plan
5. Active Suicidal Ideation with Specific Plan and Intent
6. Preparatory Acts or Behavior
7. Aborted Attempt
8. Interrupted Attempt
9. Actual Attempt (non-fatal)
10. Completed Suicide
11. Self-injurious Behavior Without Suicidal Intent

Frequency counts and percentages will be presented for subjects in each C-SSRS category, as well as subjects with any suicidal ideation (1–5), subjects with any suicidal behavior (6–10), and subjects with any suicidal ideation or behavior (1–10), by visit at which the items were collected.

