### 3. STUDY DESIGN

#### 3.1. Overview

This is a Phase 3, multi-center, open-label study to evaluate the safety and tolerability of TD9855 in subjects with primary autonomic failures (MSA, PD, and PAF) and symptomatic nOH over 182 weeks. Given the challenges presented by the COVID-19 pandemic the trial utilizes an operational design featuring the ability to conduct protocol required visits as either in clinic or remote visits. Based upon discussion with the subject, the Investigator may conduct each study visit for a given subject either in clinic or remotely. The Investigator is recommended to conduct in clinic study visits consistent either with the standard of care for a subject outside of a clinical trial or at a minimum once per year for each subject. Tools and systems are available to sites and subjects to support remote visits (e.g., direct to subject shipping of study medication and other study supplies, standardized HIPAA/GDPR compliant telemedicine platform, in-home health nurses).

Due to the potential for resurgence of COVID-19 and its impact on both sites and subjects, these tools, mechanisms, and processes will be made available to sites and subjects who have selected the in clinic visit modality.

All sites are allowed at Investigator discretion to conduct either in clinic or remote unscheduled visit(s) for subject safety or unexpected subject medical needs outside of the regular visit schedule. Data collected during these visits may include any protocol-specified assessments which will be captured in the clinical database.

Subjects who complete Study 0170 will be eligible for this study. Following signing of the informed consent, subjects will enter Study 0171 Visit 1, which will be conducted on the same day as Visit 9 of Study 0170. Study 0170 procedures conducted at Visit 9 will serve as the baseline assessments for Visit 1 of Study 0171.

Beginning on the day after Visit 1, subjects will receive a single dose of [REDACTED] TD-9855 [REDACTED] and continue thereafter for the 182-week duration of the treatment period.

Subjects will complete study visits as outlined below:

- Visit 2 (Week 2)
- Visit 3 (Week 6)
- Visit 4 (Week 10)
- Visit 5 (Week 18)
- Visit 6 (Week 26)
- Visit 7 (Week 38)
- Visit 8 (Week 50)
- Visit 9 (Week 74)
- Visit 10 (Week 98)

[figure not shown]
- Visit 11 (Week 122)
- Visit 12 (Week 146)
- Visit 13 (Week 170)
- Visit 14 (Week 182)

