### 6.4.3. Safety Assessments

#### 6.4.3.1. Columbia-Suicide Severity Rating Scale

The C-SSRS is a tool designed to systematically assess and track suicidal AEs (suicidal behavior and suicidal ideation). The strength of this suicide classification system is in its ability to comprehensively identify suicidal events while limiting the over-identification of suicidal behavior. The C-SSRS Since Last Visit Version will be used for all visits.

Assessments will be performed as specified in the Schedule of Study Procedures (Table 1). An example of the instrument is provided in Appendix 1.

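### SAP 8.8 gives C-SSRS Since Last Visit percentages only by visit, although the look-back grows from 2 to 8 weeks, and plans no whole-period C-SSRS summary

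*SAP*

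**What the plan says.** Protocol 6.4.3.1 fixes the recall period: "The C-SSRS Since Last Visit Version will be used for all visits". SAP 8.8 agrees ("The C-SSRS Since Last Visit Version will be used in this study") and says of the 11 categories: "They all have binary responses (yes/no").

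Both schedules (Protocol Table 1, SAP Table 2) place the C-SSRS at Weeks 0, 2, 6, 10, 18 and 26 and at early termination up to Week 26. The Week 14 and Week 22 telephone contacts (Protocol 6.3.6 and 6.3.8) cover only concomitant medications and adverse events. For Week 0, Protocol 3.1 says: "Study 0170 procedures conducted at Visit 9 will serve as the baseline assessments for Visit 1 of Study 0171".

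SAP 8.8 then plans counts and percentages for each category, for any ideation, for any behavior and for either, "by visit at which the items were collected". It gives no interval length, no subject-time and no summary over the treatment period.

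Two other places bear on this. Protocol 8.5 names C-SSRS among the safety variables and allows summaries either by visit or over the whole treatment period, whichever suits the data. SAP 8.7 summarizes falls over one fixed interval, Study Day 1 to Day 189.

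**The concern.** A yes on this form is an any-occurrence answer, so its probability depends on how long the period is. The period is four times as long at Weeks 18 and 26 as at Week 2. With constant risk, the percentages would step up at Week 6 and again at Week 18 simply because the question covers more time. The same lengthening could hide a real early excess.

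C-SSRS is a listed primary safety endpoint (Protocol 3.4, SAP 3.2.1). The study has a single arm, so no control column shares the schedule and shows the reader how much of a rise comes from the spacing. There is also no whole-period row to fall back on. The simplest safety question, how many subjects had any suicidal ideation or behavior on TD-9855, is not answered by any planned C-SSRS summary.

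**Working it through.** The documents give no C-SSRS event rate, so there is no stated figure to reproduce. The interval lengths come from the schedule. The event rates below are assumptions.

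**Look-back.** Differences between successive C-SSRS weeks (0, 2, 6, 10, 18, 26): 2−0 = 2, 6−2 = 4, 10−6 = 4, 18−10 = 8, 26−18 = 8 weeks.

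**Percentage expected under constant risk.** With hazard h per week and look-back L weeks, P(yes) = 1 − exp(−hL). At an assumed h = 0.0025 (0.25% per week), with all 110 enrolled subjects followed:

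| C-SSRS visit | L (weeks) | P(yes) | Expected of 110 |
|---|---|---|---|
| Week 2 | 2 | 0.50% | 0.5 |
| Week 6 | 4 | 1.00% | 1.1 |
| Week 10 | 4 | 1.00% | 1.1 |
| Week 18 | 8 | 1.98% | 2.2 |
| Week 26 | 8 | 1.98% | 2.2 |

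The ratio of Week 18 or 26 to Week 2 is (1 − exp(−0.02)) / (1 − exp(−0.005)) = 3.97. Over the 26 weeks, the proportion with any event would be 1 − exp(−0.065) = 6.3%, or about 6.9 of 110. No planned C-SSRS table shows that figure.

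**Sensitivity to the rate.** The ratio tends to 4 as h tends to 0 and falls as events become common:

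| Assumed 2-week risk | 0.1% | 1% | 5% | 10% | 20% |
|---|---|---|---|---|---|
| Ratio, 8-week to 2-week column | 3.99 | 3.94 | 3.71 | 3.44 | 2.95 |

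**Sensitivity to persistence.** Suppose a share q of subjects answers yes at every visit and the rest have a 1% 2-week risk. Then P(yes) = q + (1 − q)(1 − exp(−hL)). For q = 1%, Week 2 shows 1.99% and Week 18 shows 4.90%, a ratio of 2.46. For q = 2% the ratio is 1.97, and for q = 5% it is 1.47.

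**Sensitivity to visit timing.** The protocol allows ±3 days at Week 2 and ±7 days at Weeks 10, 18 and 26. An individual look-back can therefore be 14 ± 3 = 11 to 17 days at Week 2, and 56 ± 14 = 42 to 70 days at Weeks 18 and 26. The ratio of the two can range from 42/17 = 2.5 to 70/11 = 6.4. If subjects took the Week 14 and 22 calls as the last visit, the later look-backs would be 4 weeks and the ratio about 2. The schedule places no C-SSRS at those calls, so 8 weeks is the natural reading.

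**Check on dividing by time.** For new events at 0.25% per week, dividing by look-back gives 0.50/2 = 0.25 and 1.98/8 = 0.25 per 100 subject-weeks, which is flat, as it should be. If instead 1% of subjects are persistently positive and nobody else is, the same division gives 1/2 = 0.5 at Week 2 and 1/8 = 0.125 at Weeks 18 and 26. That is a false fourfold decline, so a rate must count newly positive subjects only.

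**The case against.** The case for leaving SAP 8.8 alone has real weight.

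- **The table is descriptive.** SAP 8.8 plans no trend test and no comparison between visits. A reader might infer that the plan treats the columns as comparable, but it does not say so. This stands: the risk lies in how the table is read, and no estimate or test is affected.
- **The numbers are small.** At the assumed rate, the fourfold ratio is a difference of under two subjects, and attrition would shrink it further. This also stands. It limits the practical effect but does not supply the missing whole-period figure.
- **The nominal look-backs can be recovered.** It is tempting to say that a reader cannot undo the artefact. In fact the columns are visit weeks, the form's name states its recall period, and the schedule is in the SAP. What the table does not show is the actual intervals after early, late or missed visits, although the listings would contain the dates.
- **Other tables help.** Suicidality recorded as an adverse event also enters the treatment-emergent tables of SAP 8.1, which do not depend on C-SSRS spacing. That is a partial safeguard, since it depends on the event being recorded as an adverse event.

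A reader might also infer that falls share the problem, because Protocol 8.5.7 refers to the "number and percentage of subjects with at least 1 fall since the previous study visit". The plan does not support that. Protocol 8.1 leaves changes of analysis to the SAP, and SAP 8.7 counts falls over one fixed interval and plans no by-visit falls table.

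**Conclusion.** The point holds for C-SSRS only, as a matter of presentation and completeness. SAP 8.8 sets side by side percentages that cover 2, 4, 4, 8 and 8 weeks, without saying so, and offers no summary over the treatment period.

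Four is the limit of the distortion at nominal visit times, for rare, new events at constant risk. A reader might take it as the rise that will appear, but the documents do not support that. They give no event rate, and the calculated ratio drops to between 2.46 and 1.47 when 1% to 5% of subjects are persistently positive alongside a 1% 2-week risk. At an assumed 0.25% per week with all 110 subjects followed, the expected counts are about 0.5 at Week 2 and 2.2 at Weeks 18 and 26.

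The change is still worth making. This is a listed primary safety endpoint in an uncontrolled study, and the SAP already handles falls over a fixed interval.

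**What to change.** In SAP 8.8:

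1. Add a summary of subjects with any post-baseline suicidal ideation, any behavior, and either, over Study Day 1 to Day 189, with the number assessed as denominator. State that it uses every post-baseline C-SSRS in that interval. Otherwise the general rule in SAP 6 would exclude assessments that fall between the windows of SAP Table 4.
2. Label each by-visit column with its nominal look-back (2, 4, 4, 8 and 8 weeks), note that the Week 0 form looks back into Study 0170, and add a footnote that columns of different length are not directly comparable.
3. If a time course is wanted, show beside the raw percentages the newly positive subjects per 100 subject-weeks, with time counted from each subject's actual previous C-SSRS date. Define newly positive as having no earlier positive answer in this study, and remove subjects from the denominator once positive. Do not divide all positives by look-back time, because persistent ideation would then appear to decline.

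The cost is SAP wording, one derived variable from dates already collected, and one or two extra rows or columns in a descriptive table. No new data are needed, and the falls analysis in SAP 8.7 needs no change on this account.
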